8.3 Data Analysis Plans

An exact test for a single proportion will be used to test the hypothesis that the CR rate at 6 months for the group as a whole is greater than 50%. The CR rates at 6 months for the group as a whole and for the CAH and grade 1 EC patients separately will also be estimated and reported along with exact 95% confidence intervals. Patients who progress at 3 or 6 months will be considered non-responders and will be included in these analyses. Patients who fail to complete 3 months of metformin therapy, for reasons unrelated to disease progression or activity, will not be included. The CR rate at 12 months will also be estimated and the analysis will include all patients who had at least 3 months of metformin therapy.

Patient adherence will be described by the percentage of patients able to adhere to at least 80% of planned metformin doses over the course of treatment. The adherence rate will be estimated and reported along with an exact 95% confidence interval. All patients who initiated treatment on study will be included in this analysis. Adverse events will be described by type and grade using frequency tables.

Changes in Ki-67 from baseline to 6 months will be analyzed using a paired t-test or the Wilcoxon signed-rank test as appropriate. Fisher's exact tests will be used to explore associations between expression (via IHC) of the metformin transporter proteins and key targets of the metformin/mTOR signaling pathway and CR at 6 months. Two-sample t-tests will be used to explore associations between metabolic factors and CR. Correlation coefficients and regression models will be used to explore associations between metabolic factors and metformin concentration levels in tumor tissue. Profiling of metabolites and all associated metabolomic analyses will be conducted by the UNC NORC/Nutrition Research Institute Metabolomics Core.

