2.3 Exploratory Objectives

- 2.3.1** To explore changes in cellular proliferation as measured by the marker, Ki-67, from baseline to 6 months
- 2.3.2** To explore association between the level of expression of the metformin transporter proteins and key targets of the metformin/mTOR signaling pathway and CR status at 6 months
- 2.3.3** To perform a comprehensive unbiased profiling of metabolites by analyzing the metabolic “fingerprints” of the biofluids (i.e. serum and urine) and “footprints” of the tumor tissue pre- and post- 6 months of metformin treatment
- 2.3.4** To explore association between metabolic factors and metformin concentration levels in tumor tissue/blood/urine and CR at 6 months

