Immunohistochemical Analysis: Tissue microarrays will be constructed and immunohistochemical analysis will be performed to assess expression of the key components of the metformin/mTOR, including AMPK, LKB1, Akt, PTEN, S6K1 and 4E-BP1. Phosphorylated and non-phosphorylated forms of these proteins will be evaluated. Expression of the metformin transporter proteins will also be assessed by immunohistochemical analysis, including OCT1-3, MATE1/2 and PMAT. Stained slides will be visually scored by experienced observers blinded to the type of antibody used and to the identity of the tissue sections. Individual slides will be digitized using the Aperio ScanScope (Aperio Technologies, Vista, CA), and digital images will be analyzed using Aperio ImageScope software.

Metformin Transporter mRNA Expression in Endometrial Tissues. Total RNA will be isolated from EH paraffin-embedded tissues and subjected to RT-PCR for determination of metformin transporter mRNA expression, including OCT1-3, MATE1/2 and PMAT. The relative mRNA levels for individual transporters will be normalized to the 18s rRNA housekeeping gene.

Metabolomic Analysis: We will perform comprehensive metabolomic analysis of serum and urine to identify potential biomarkers responsive to metformin treatment using mass spectrometry. These analyses uncover the subtle differences between the spectra that correlate to the disease or treatment under study revealing metabolomic “footprints” (from tissue) and “fingerprints” (from biofluids). Thus, a comprehensive unbiased profiling of metabolites (molecule weight<1000 Dalton) will be performed, and we will analyze the metabolic “fingerprints” of the biofluids (i.e. serum and urine) of women with endometrial hyperplasia/cancer, pre- and post- 6 months of metformin treatment. Time of flight mass spectrometry (TOF-MS) coupled to chromatographic separations including gas chromatography (GC-TOF-MS, Leco Corp.) and liquid chromatography (LC-TOF-MS, Agilent Corp.) will be used for the measurement of tumor specimens and biofluids, and these analyses will be conducted according to previously developed methods by the UNC NORC/Nutrition Research Institute Metabolomics Core. Significant variables (metabolite markers) will be selected

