8.2 Sample Size, Stopping Rule, and Accrual

The goal accrual is 32 patients (16 CAH, 16 EC) and we expect to enroll 1-2 patients/per month. Our power calculation and analysis will be based on 30 patients, assuming early discontinuation of 2 participants prior to 3 months of treatment. We estimate 18 months to complete accrual.

The primary objective of this study is to compare the CR rate at 6 months to a rate of 50% (the 50% is based on results reported in the meta-analysis referenced earlier, and because a response rate significantly greater than this will be considered clinically meaningful by the investigators). With a combined sample size of 30 evaluable patients with either CAH or grade 1 EC, and assuming a null CR rate of 50% and an alternative of 75%, we will have 80% power to conclude that the CR rate at 6 months is significantly higher than 50% using an exact test for a single proportion with a two-sided α of 0.05. Furthermore, the exact 95% confidence interval for the CR rate at 6 months will have a maximum width of 0.374. This means that the CR rate will be estimated within at least 18.7%. CAH and grade 1 EC represent a spectrum of neoplasia, which is why the two groups are being combined for the primary objective. The CR rate at 6 months will be estimated separately in the CAH and EC groups as a secondary objective.

Sequential boundaries will be used to suspend the trial if excessive toxicity is seen that requires discontinuation of metformin. If the study reaches a stopping boundary, it may be terminated by the PI, or submitted to the DSMC with a description of the toxicities and a rationale for why the study should be continued. At the patient level, metformin will be discontinued if a patient experiences: (1) a single grade 3 or higher metformin-related GI disturbance or grade 4 or higher hypoglycemic episode, or (2) two or more grade 2 side effects considered related to metformin therapy, or (3) if the patient requires a dose less than 850mg once daily. The accrual will be halted if the number of patients discontinuing metformin for one of the reasons above is equal to or exceeds b_n out of n patients who have been followed for toxicity for 3 months. This is a Pocock type stopping

boundary that assumes that a metformin discontinuation rate of 0.25 is acceptable, but anything $>25\%$ is unacceptable. If the true toxicity rate is equal to 0.25, the probability of crossing the boundary is 0.05.

Stopping Rule

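### Section 8.3 tests immunohistochemical expression against complete response with Fisher's exact test, without defining the categories; a rank test on the recorded score would be more powerful at no cost (minor, exploratory).

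*Combined protocol and SAP*

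**What the plan says.** Objective 2.3.2 reads "To explore association between the level of expression of the metformin transporter proteins and key targets" of the metformin/mTOR pathway, against CR status at 6 months. Section 8.3 assigns the test: Fisher's "exact tests will be used to explore associations between expression (via IHC) of the metformin transporter proteins" and of the pathway targets, against CR at 6 months.

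Section 6.7 describes the measurement. On the transporters it says: "Expression of the metformin transporter proteins will also be assessed by immunohistochemical analysis, including OCT1-3, MATE1/2 and PMAT". On reading the slides: "Stained slides will be visually scored by experienced observers blinded to the type of antibody used and to the identity of the tissue sections". The slides are also digitised, and "digital images will be analyzed using Aperio ImageScope software". No scoring scale, positivity definition, category rule or cut-point is given for these markers in section 6.7 or 8.3, and the variable that the image software is to deliver is not named.

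Other correlates in section 8.3 are analysed as measured values. Metabolic factors are compared with CR by two-sample t-test, and the change in Ki-67, which section 6.7 defines as a percentage of positive cells, by paired t-test or signed-rank test.

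**The concern.** The question is about level, and the described methods can yield a level, but the chosen test works on a table of categories. Two things follow.

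- The test cannot be run on a graded or continuous score until someone decides how to group it. The plan leaves that decision open, including whether it comes before or after CR status is known.
- Even with sensible groups, Fisher's test treats them as unordered and so gives up information that a rank test would use. With about 30 women, that information is worth keeping.

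At stake is whether objective 2.3.2 can detect a marker that matters, and whether a marker reported as associated with CR can be believed. The trial's main conclusion is not at stake.

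**Working it through.** **Inputs from the documents.** Section 8.2 gives the number: "With a combined sample size of 30 evaluable patients with either CAH or grade 1 EC", from 32 accrued, "assuming early discontinuation of 2 participants prior to 3 months of treatment". It also gives the CR rates, "assuming a null CR rate of 50% and an alternative of 75" per cent. These set the group sizes: 30 × 0.50 = 15 v 15, and 30 × 0.75 = 22.5, taken as 22 v 8.

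**The plan's own figures.** The plan gives no power, alpha or effect size for the expression tests. Its primary figures reproduce: rejecting at 21 or more CRs out of 30 has an upper tail of 0.0214 under 50% (within 0.025) and power 0.803 under 75%, against the stated 80%. The exact 95% interval at 15/30 runs from 0.313 to 0.687, a width of 0.374 as stated.

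**Assumptions, not in the documents.** A graded score is recorded; it is normally distributed and shifted by d SD between CR and non-CR; testing is two-sided at 0.05.

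**Large-sample efficiency.** A cut at quantile q, relative to the t-test, keeps φ(z_q)² / [q(1−q)]. The Wilcoxon test keeps 3/π = 0.955. So relative to Wilcoxon:

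- q = 0.50: 0.637 / 0.955 = 0.67, a loss of about one third.
- q = 0.75: 0.539 / 0.955 = 0.56.
- q = 0.80: 0.490 / 0.955 = 0.51.
- q = 0.90: 0.342 / 0.955 = 0.36.

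**Power with 30 patients** (simulation, 3,000 data sets per row; repeat runs move the figures by up to about two points, for example 33-84% v 53-97% at 15 v 15 and 28-76% v 42-92% at 22 v 8):

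| CR v non-CR | d (SD) | Fisher, median split | Wilcoxon, measured score | Fisher, 4-level score | Wilcoxon, 4-level score |
|---|---|---|---|---|---|
| 15 v 15 | 0.8 | 32.1% | 53.1% | 34.8% | 49.8% |
| 15 v 15 | 1.0 | 48.3% | 71.8% | 49.6% | 68.5% |
| 15 v 15 | 1.2 | 64.0% | 87.1% | 67.9% | 83.4% |
| 15 v 15 | 1.5 | 84.4% | 97.5% | 86.5% | 96.4% |
| 22 v 8 | 0.8 | 27.9% | 41.0% | 25.6% | 38.6% |
| 22 v 8 | 1.0 | 41.5% | 61.9% | 38.7% | 58.1% |
| 22 v 8 | 1.2 | 55.3% | 75.1% | 53.2% | 71.6% |
| 22 v 8 | 1.5 | 74.6% | 91.4% | 73.8% | 89.5% |

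The gain over a median split is 13 to 24 points. On a 4-level ordinal score, where Fisher's test is used in its multi-category form, the gain is 10 to 19 points. With a cut at the 75th percentile and d = 1.0, Fisher's power falls to 31.7% (15 v 15) and 7.5% (22 v 8).

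**In patients.** At 15 v 15 and d = 1.0, Fisher's 48.3% lies between Wilcoxon with 9 per group (45.0%) and 10 per group (51.2%). So 30 patients do the work of about 19 to 20. With the 75th-percentile cut, 31.7% lies between 6 per group (30.0%) and 7 per group (33.8%), or about 12 to 13 patients.

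**False positives.** With no true difference and the cut fixed at the median, Fisher's rate is 2.9% (15 v 15) and 3.5% (22 v 8). If the cut with the smallest p-value were picked from the data, the rate per marker would be 7-15% at 15 v 15, about 18% at 22 v 8, and 14-22% at 20 v 10. The spread reflects how far from the centre the search is allowed to go.

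**The case against.** Several objections are fair.

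- **The plan does not say that expression will be dichotomised.** A reader might infer a high/low split from the choice of test, but Fisher's test can take more than two categories. This stands. The point survives it, because the rank test also gains on a 4-level score.
- **The plan does not say that a cut will be chosen after seeing the data.** It is silent on when and how categories are set. The 7-22% range is what would follow from a best-cut search, which the plan does not propose. The blinding of the scorers protects the scoring, but it does not settle who chooses the grouping or when.
- **A reader might infer that most of the information is thrown away.** A median split loses about one third. Losing more than half takes an off-centre cut, at about the 75th percentile in the 30-patient simulation and beyond the 80th in large samples.
- **A more dramatic contrast appears at 20 v 10**, where a median split gives Fisher about 21% power against 66% for the rank test at 1 SD. That is an artefact of discreteness: with 8 of the 10 non-CR patients on one side of the cut, p = 0.0502, so the test's actual size there is about 0.5%. Nor is 20 v 10 one of the scenarios in section 8.2.
- **Fisher's test is valid, and the analysis is exploratory.** Both stand. The rank test is a gain in efficiency and not the repair of an invalid test. For a marker recorded only as positive or negative, it gains nothing.

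**Conclusion.** The point holds as a minor one. Objective 2.3.2 asks about level, the described methods can measure it, and section 8.3 names a test that needs undefined categories and ignores their order. At the two group splits implied by section 8.2, a rank test on the recorded score gains roughly 13 to 24 percentage points of power over Fisher's test at a median split, for assumed shifts of 0.8 to 1.5 SD. Put differently, about one third of the effective sample size is saved, and more if the cut would have been off-centre.

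This rests on a graded score being recorded, on an association that runs in one direction, and on effect sizes that the documents do not supply. The documents do not support saying that the plan dichotomises, that it discards most of the information, or that it will inflate false positives. The last is a risk that the plan leaves open. The primary, secondary and safety results do not depend on this analysis.

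**What to change.** In section 8.3, replace the sentence on Fisher's test with one to this effect: for each marker, the recorded score or percent-positive value will be compared between patients with and without CR at 6 months by the Wilcoxon rank-sum test, in its exact form allowing for ties; Fisher's exact test will be used only for markers recorded as present or absent, with the definition of present fixed before expression data are linked to CR status.

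Section 6.7 should name, for each marker, the scale and whether the visual score or the image-analysis value is the one analysed.

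The cost is a sentence or two. No further data, patients or procedures are needed.

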9.0 STUDY MANAGEMENT

9.1 Institutional Review Board (IRB) Approval and Consent

It is expected that the IRB will have the proper representation and function in accordance with federally mandated regulations. The IRB should approve the consent form and protocol.

In obtaining and documenting informed consent, the investigator should comply with the applicable regulatory requirement(s), and should adhere to Good Clinical Practice (GCP) and to ethical principles that have their origin in the Declaration of Helsinki.

Before recruitment and enrollment onto this study, the patient will be given a full explanation of the study and will be given the opportunity to review the consent form. Each consent form must include all the relevant elements currently required by the FDA Regulations and local or state regulations. Once this essential information has been provided to the patient and the investigator is assured that the patient understands the implications of participating in the study, the patient will be asked to give consent to participate in the study by signing an IRB-approved consent form.

Prior to a patient's participation in the trial, the written informed consent form should be signed and personally dated by the patient and by the person who conducted the informed consent discussion.

9.2 Required Documentation

Before the study can be initiated at any site, the following documentation must be provided to the Clinical Protocol Office (CPO) at the University of North Carolina.

- A copy of the official IRB approval letter for the protocol and informed consent
- IRB membership list
- CVs and medical licensure for the principal investigator and any sub-investigators who will be involved in the study.
- Form FDA 1572 appropriately filled out and signed with appropriate documentation (NOTE: this is required if UNC holds the IND. Otherwise, the Investigator's signature documenting understanding of the protocol and providing commitment that this trial will be conducted according to all stipulations of the protocol is sufficient to ensure compliance)
- CAP and CLIA Laboratory certification numbers and institution lab normal values
- Executed clinical research contract

9.3 Registration Procedures

All patients must be registered with the CPO at the University of North Carolina before enrollment to study. For UNC patients, prior to registration, eligibility

criteria must be confirmed with the UNC Study Coordinator. To register a patient, call the Oncology Protocol Office at [contact] Monday through Friday, 9:00AM-5:00PM.

For Affiliate patients, to register and confirm patient eligibility, please fax registration forms, informed consent, and source documents to [contact], or scan and email to the project manager (preferred).

9.4 Data Management and Monitoring/Auditing

The CPO of the UNC LCCC will serve as the coordinating center for this trial. Data will be collected through a web based clinical research platform, OnCore®. UNC personnel will coordinate and manage data for quality control assurance and integrity.

All data will be collected and entered into OnCore® by Clinical Research Associates (CRAs) from UNC LCCC and participating institutions. The investigators at each site will allow monitors to review all source documents supporting data entered into OnCore®. The UNCCN Data Coordinator can be reached at [contact] or [name].

As an investigator initiated study, this trial will also be audited by the Lineberger Cancer Center audit committee every six or twelve months, depending on the participation of affiliate sites.

9.5 Adherence to the Protocol

Except for an emergency situation in which proper care for the protection, safety, and well-being of the study patient requires alternative treatment, the study shall be conducted exactly as described in the approved protocol.

9.5.1 Emergency Modifications

UNC and Affiliate investigators may implement a deviation from, or a change of, the protocol to eliminate an immediate hazard(s) to trial subjects without prior UNC or their respective institution's IRB/IEC approval/favorable opinion.

For Institutions Relying on UNC's IRB:

For any such emergency modification implemented, a UNC IRB modification form must be completed by UNC Research Personnel within five (5) business days of making the change.

For Institutions Relying on Their Own IRB:

For Affiliate investigators relying on their own institution's IRB, as soon as possible after the modification has been made, the implemented deviation or change and the reasons for it should be submitted to:

- To UNC Principal Investigator for agreement

- The Affiliate institution's IRB for review and approval. (Once IRB's response is received, this should be forwarded to the UNCCN Regulatory Associate).

9.5.2 Single Patient/Subject Exceptions

For Institutions Relying on UNC's IRB:

Any request to enroll a single subject who does not meet all the eligibility criteria of this study requires the approval of the UNC Principal Investigator and the UNC IRB.

For Institutions Relying on Their Own IRB:

Any request to enroll a single subject who does not meet all the eligibility criteria of this study requires the approval of the UNC Principal Investigator and the participating institution's IRB, per its policy. Please forward the IRB response to the UNCCN Regulatory Associate by facsimile or via email within 10 business days after the original submission.

9.5.3 Other Protocol Deviations/Violations

According to UNC's IRB, a protocol deviation is any unplanned variance from an IRB approved protocol that:

- Is generally noted or recognized after it occurs
- Has no substantive effect on the risks to research participants
- Has no substantive effect on the scientific integrity of the research plan or the value of the data collected
- Did not result from willful or knowing misconduct on the part of the investigator(s).

An unplanned protocol variance is considered a violation if the variance meets any of the following criteria:

- Has harmed or increased the risk of harm to one or more research participants.
- Has damaged the scientific integrity of the data collected for the study.
- Results from willful or knowing misconduct on the part of the investigator(s).
- Demonstrates serious or continuing noncompliance with federal regulations, State laws, or University policies.

If a deviation or violation occurs please follow the guidelines below:

For Institutions Relying on UNC's IRB:

Protocol Deviations: UNC or Affiliate personnel will record the deviation in OnCore®, and report to any sponsor or data and safety monitoring committee in accordance with their policies. Deviations should be summarized and reported to the IRB at the time of continuing review.

Protocol Violations: Violations should be reported by UNC personnel within one (1) week of the investigator becoming aware of the event using the same IRB online mechanism used to report Unanticipated Problems.

For Institutions Relying on Their Own IRB:

In addition to adhering to the policies regarding protocol compliance set forth by your institution's IRB, the following is also required:

Protocol Deviations: In the event a deviation from protocol procedures is identified, record the deviation in OnCore®.

Protocol Violations: Any protocol violation that occurs must be reported to your IRB per institutional policies and reported to the UNCCN Project Manager within 5 days. UNC-CH will determine if the violation affects the safety of the patient and integrity of the data. Once your institution's IRB response is received, please forward to the UNCCN Regulatory Associate.

Unanticipated Problems:

Affiliate Sites:

Any events that meet the criteria for “Unanticipated Problems (UPs)” as defined by UNC’s IRB must also be reported to the UNCCN Project Manager. The UNCCN Project Manager will report the event to the UNC IRB using the IRB’s web-based reporting system. Examples of such UPs include a lost or stolen laptop computer that contains sensitive study information.

UNC

Any events that meet the criteria for “Unanticipated Problems” as defined by UNC’s IRB must be reported by the Study Coordinator using the IRB’s web-based reporting system.

